## Data Analysis

**Primary Statistical Methods & Software:** All outcomes will be analyzed at the participant level. Analyses will employ population-averaged marginal models estimated by Generalized Estimating Equations (GEE) to account for correlations among the within-person baseline and follow-up measurements. Marginal models estimated by GEE are advantageous for their population-level interpretation and robustness of estimated effects to the assumed correlation structure among repeated measurements (meaning unbiased estimates of the effect of the behavioral intervention will be obtained whether or not the correlation among repeated measurements within a participant is modeled correctly). Clusters will be defined at the level of the participant for all analyses, and independent working correlation will be assumed. Linear models will be used for continuous outcomes and logistic models for categorical or ordinal outcomes. Analyses will be conducted using Stata.

Models will include intervention, measurement timepoint, and the interaction of intervention and measurement timepoint as categorical variables. The primary analysis testing the effectiveness of the cash transfers compared to the control arm will be evaluated by the test of the null hypothesis that the intervention-measurement timepoint interaction coefficient is 0, denoting no difference in the change in respective outcomes from baseline to month 3 between intervention and control. The Holm procedure at a family-wise error rate of 0.05 will be used to account for multiple comparisons in testing differences in the 8 primary outcomes between the two groups.

**Exclusion Criteria & Restrictions:** Physician co-investigators will clarify any values that appear out of range (e.g., biologically implausible values) prior to excluding any data. Any data that are excluded will be done prior to re-matching participants to study arm.

**Assumption Checking & Data Cleaning:** Data will be descriptively summarized and evaluated for quality prior to analyses. Means and standard deviations will be used to characterize continuous variables such as weight and blood pressure, and frequencies and percentages will be used to describe categorical variables. Medians and interquartile ranges will be reported for continuous variables that exhibit skewness. Data will be descriptively summarized overall and by study arm.

As a manipulation check, we can also download the Clincard data to see how much money is left on people's cards at the end of the study.

**Missing Data:** Although we expect to have minimal missing data because most questionnaire items are required, we will consider other analytic techniques like inverse probability of weighted GEE and multiple imputation to handle missing data (e.g., due to loss to follow-up) if the amount is greater than 10%.

**Secondary Analyses:** *[Could be subgroup analyses, sensitivity analyses, exploratory analyses]*

- If there is enough variation in moderators, exploratory moderation analyses will test how they impact the main effect. Given the pilot nature of this study, we will focus first on household income % of the federal poverty line, but other moderators will be considered.
- Our 10 secondary outcomes include:
  1. number of Emergency Department (ED) visits (from the Electronic Health Record (EHR))
  2. number of non-ED visits (EHR)
  3. smoking (5-25, Cigarette Dependence Scale, short version (CDS-5))
  4. alcohol use (0-12, Alcohol Use Disorders Identification Test (AUDIT-C))
  5. all health care expenditures (raw dollars, medications + office visits + ER visits)
  6. time preference: patience item (0-10)
  7. time preference: behavioral choice task (binary)
  8. Kessler Psychological Distress Scale (6-30, K6+)
  9. self-reported number of healthy days from (CDC health-related quality of life HRQOL-4)
  10. medication taking adherence subscale (ARMS)
- Exploratory health outcomes include objectively measured body mass index and systolic and diastolic blood pressure.
- Secondary analyses of medication adherence will compare the self-reported medication adherence refills (ARMS) to EHR frequency of medication refills (i.e., combining medication name, recommended frequency of use, quantity prescribed, number of refills per prescription, and refill start date) as a proxy for adherence. Note: Refills are requested by pharmacies or patients, so pharmacy refill requests could bias toward adherence.
  - If there is a strong relationship between the ARMS and the EHR prescription measure, we will analyze the EHR prescription measure as a secondary outcome.
- We will assess whether the Acceptability of Intervention Measure (4-item mean, 1-5) varies by any demographic characteristics.

**Table Shells:** *[Not required to include these, but they may help focus the analysis plan, or help get the paper started]*

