  - W9 (including SSN) and C2 will be collected for all participants . These will be completed by paper and stored in a secure location only accessible by study

personnel. At the end of the study, W9 forms will be scanned and sent via SecureShare to [name] to be logged into the Greenphire W-9 Database. Once scanned, paper copies will be shredded.

At the end of the baseline assessment, participants will be randomized using a permuted block technique with block size of 4 to either usual care (Arm 1) or to the unconditional cash transfer intervention (Arm 2). Participants in Arm 2 will receive an unconditional cash transfer of \$125 every 2 weeks for 8 payments via ClinCard, for a total of \$1000. In addition, 16 participants will also be randomly selected to receive a blood pressure cuff to take home. Of these 16, 8 will be blood pressure cuffs that wirelessly transmit readings to an app on their mobile phone. Participants that receive a blood pressure cuff will be asked to take a blood pressure reading weekly for the duration of their enrollment period, and record their reading via a REDCap survey link sent by text. Those receiving a wireless blood pressure cuff will transmit their readings wirelessly, as well as record their reading in the weekly REDCap survey link. The goal of this procedure is to pilot test the feasibility of this technology and approach for a future, larger study.

All participants will be asked to return for an in-person assessment at month 3. This assessment will include all elements of the baseline assessment. Additionally, intervention participants will complete the Acceptability of Intervention Measure and be asked a survey question about how the cash transfer was used. Participants randomized to receive a blood pressure cuff will also be asked to complete a short survey regarding their acceptability and use of a blood pressure cuff at home.

Via ClinCard, all participants will receive \$25 compensation for completing the baseline assessment, and \$50 for completing the follow-up assessment. Participants providing at-home blood pressure readings will receive an additional \$3 per reading (maximum \$3 per week, \$48 total).

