## 7. Analysis Plan

AIMS 1 & 2: Data will be descriptively summarized and evaluated for quality prior to analysis. Means and standard deviations will be used to characterize continuous variables such as weight and blood pressure, and frequencies and percentages will be used to describe categorical variables. Medians and interquartile ranges will be reported for continuous variables that exhibit skewness. Data will be descriptively summarized overall and by condition.

All outcomes will be analyzed at the participant level. Analyses will employ population-averaged marginal models estimated by Generalized Estimating Equations (GEE) to account for correlations among the within-person baseline and follow-up measurements. Marginal models estimated by GEE are advantageous for their population-level interpretation and robustness of estimated effects to the assumed correlation structure among repeated measurements (meaning unbiased estimates of the effect of the behavioral intervention will be obtained whether or not the correlation among repeated measurements within a participant is modeled correctly). Clusters will be defined at the level of the participant for all analyses, and independence working correlation will be assumed. Linear models will be used for continuous outcomes and logistic models for categorical or ordinal outcomes.

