Models will include intervention, measurement timepoint, and the interaction of intervention and measurement timepoint as categorical variables. The primary analysis testing the effectiveness of the cash transfers compared to the control arm will be evaluated by the test of the null hypothesis that the intervention-measurement timepoint interaction coefficient is 0, denoting no difference in the change in respective outcomes from baseline to month 3 between intervention and control. We will evaluate the sensitivity of estimated intervention effects to imbalances in baseline covariates and missing data. To assess the impact of imbalance in baseline covariates, outcomes will be reanalyzed in models that adjust for baseline covariates that differ significantly at the 0.05 level by condition. We will evaluate sensitivity to missing data by inverse probability of weighted GEE and multiple imputation. The Holm procedure at a family-wise error rate of 0.05 will be used to account for multiple comparisons in testing differences in 9 primary outcomes between the two groups (number of ED visits, number of non-ED visits, medication adherence, smoking, alcohol use, food security, utility security, health expenditures, and financial stress).

Aim 3 – Qualitative interviews: Qualitative analyses will be guided by an integrated approach that includes identification of a priori attributes of interest and identification of emergent codes and themes. A comprehensive coding scheme will be developed and applied to all data to produce a fine-grained descriptive analysis. All transcribed interview data will be imported into Nvivo for thematic coding. A single analyst will review and code all transcripts. The analysis will yield an understanding of any unanticipated or anticipated consequences of the study and cash transfer provision while also elucidating pathways through which cash transfers influence health behavior.

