**Covariates:** To assess the impact of imbalance in baseline covariates, outcomes will be reanalyzed in models that adjust for baseline covariates that differ significantly at the 0.05 level by study arm. These include:

- Sociodemographics: age, sex, gender, low-income vs other-income zipcode, race, ethnicity, sexual orientation, marital status, schooling attainment, being a parent, number of children
- Economic data: work, income sources (including government programs such as SNAP, TANF, and WIC), and total household income
- Housing data: living situation, household composition, and housing security
- Number of chronic medications
- Chronic medical conditions (problem list) – especially the 3 inclusion criteria: prediabetes, diabetes, and hypertension

**Potential Moderators:** In exploratory analyses, to examine whether the intervention impacts health inequities within the sample population, we will assess the intervention effects on physical and mental health across several sociodemographic categories (as tested in Jaroszewicz et al, 2022 RCT with 5,243 participants; \$500 or \$2000 one-time transfers (participant median monthly income = \$1000)).

- Gender (binary: female)
- Race (binary: not exclusively white)\*
- Age (continuous)
- SES
  - Household income level as % FPL (continuous)
  - Yost SES Quintile (binary: lowest vs other; factor analysis of 7 ACS variables; used by SEER; instead of ADI based on Boscoe et al, 2021)
  - Income sources (binary: received governmental assistance at baseline)
  - Work (binary: being employed at baseline)

- Schooling attainment (binary: completed at least high school)
- Family structure
  - Being a parent (binary)
  - Number of children (continuous)
  - Fraction of one's children who are male (proportion)\*
  - Marital status (binary: having a partner or spouse)\*

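### For the linear-model primary outcomes, the planned arm-by-time test is valid but gives up precision that adjusting month 3 for the outcome's own baseline value would recover

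*SAP*

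**What the plan says.** Section 7 of the protocol and the SAP's Data Analysis section specify the same primary analysis. It is a GEE with the participant as cluster, and "independence working correlation will be assumed" (protocol). On terms, the SAP says: "Models will include intervention, measurement timepoint, and the interaction of intervention and measurement timepoint as categorical variables". The null hypothesis is a zero interaction, "denoting no difference in the change in respective outcomes from baseline to month 3 between intervention and control" (protocol). On link functions: "Linear models will be used for continuous outcomes and logistic models for categorical or ordinal outcomes" (SAP).

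Among the SAP's eight primary outcomes, the linear model clearly applies to financial well-being, perceived stress, state anxiety and the medication-refill subscale. It also applies to vigilance-task lapses and medication dollars if these are treated as continuous, which the SAP does not state. Food and utility security are categorical and get logistic models; they are outside this point.

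Section 5.1 of the protocol fixes the order of events: "At the end of the baseline assessment, participants will be randomized using a permuted block technique with block size of 4". Allocation is 50 and 50.

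Baseline covariates enter only a sensitivity model: "outcomes will be reanalyzed in models that adjust for baseline covariates that differ significantly at the 0.05 level by study arm" (SAP, Dataset, Covariates). The list there does not include the baseline value of the outcome being analysed.

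**The concern.** Both documents defend GEE because its estimates stay unbiased whatever the working correlation. Neither discusses precision. Because the model has a free arm main effect, the baseline difference between arms is estimated and subtracted in full. After randomisation that difference is pure chance. Subtracting all of it helps only as far as baseline predicts month 3; beyond that it adds noise. Regression on baseline subtracts only the predictive part.

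Section 2 of the protocol names finding plausible effect sizes for a larger trial as one goal of this pilot. The width of the intervals around those effects is therefore a main product of the study, and baseline data already planned can narrow it. Holm over eight outcomes makes lost precision costlier, since the smallest p-value must pass 0.05/8 = 0.00625.

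**Working it through.** **Inputs.** From the documents: n = 50 per arm, 1:1 allocation, two visits, eight primary outcomes under Holm at 0.05, and a 10% missing-data threshold. Assumed, because the documents do not give them: the baseline to month-3 correlation rho, the SD ratio k = month-3 SD / baseline SD, a 0.5 SD effect for power, two-sided tests, and cluster-robust standard errors for the GEE. The plan states no precision or power figure to reproduce.

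**Step 1: what the interaction is.** In a fitted example with complete data, the GEE interaction and its robust SE equalled the difference in mean change and its SE exactly.

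**Step 2: variances**, in units of the baseline SD squared, complete data, large samples.
- Planned: (2/n)(1 + k² − 2·rho·k)
- Month 3 on arm and baseline: (2/n)·k²(1 − rho²)
- Ratio: (1 + k² − 2·rho·k) / [k²(1 − rho²)]

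Numerator minus denominator is (1 − rho·k)², which is never negative. At k = 1 the ratio is 2(1 − rho)/(1 − rho²) = 2/(1 + rho).

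**Step 3: missing month-3 values.** Let a fraction f have a month-3 value, missing completely at random. The independence GEE uses all baselines; the regression uses completers only. The ratio becomes (k² + f − 2f·rho·k) / [k²(1 − rho²)]. Numerator minus denominator is (k·rho − f)² + f(1 − f), again never negative.

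**Step 4: variance ratios, planned / adjusted.**

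| Setting | rho 0.3 | 0.5 | 0.7 | 0.9 |
|---|---|---|---|---|
| k = 1, complete | 1.54 | 1.33 | 1.18 | 1.05 |
| k = 0.8, complete | 1.99 | 1.75 | 1.59 | 1.64 |
| k = 1.25, complete | 1.27 | 1.12 | 1.02 | 1.05 |
| k = 1, f = 0.9 | 1.49 | 1.33 | 1.25 | 1.47 |

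Example: k = 0.8, rho = 0.5 gives (1 + 0.64 − 0.80)/(0.64 × 0.75) = 0.84/0.48 = 1.75. The loss need not shrink as rho approaches 1.

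At k = 1 the planned 100 participants are worth 100(1 + rho)/2 = 65, 75, 85 and 95 under adjustment. The planned variance relative to comparing month-3 means alone is 2(1 − rho), so below rho 0.5 the plan is less precise than ignoring baseline.

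**Step 5: intervals and power at k = 1, complete data.** The SE is √[0.04 × 2(1 − rho)] planned and √[0.04(1 − rho²)] adjusted. Half-width is 1.96 × SE. Power at the first Holm step is Φ(0.5/SE − 2.734).

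| rho | 95% half-width in SD, planned v adjusted | Power, planned v adjusted |
|---|---|---|
| 0.3 | 0.46 v 0.37 | 26.7% v 45.5% |
| 0.5 | 0.39 v 0.34 | 40.7% v 56.1% |
| 0.7 | 0.30 v 0.28 | 68.9% v 77.8% |
| 0.9 | 0.175 v 0.171 | both above 99% |

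**Step 6: simulation at 50 per arm** (20,000 trials, true effect 0.5 SD). Mean estimates were 0.498 to 0.503 for both methods. Ratios at rho 0.3, 0.5, 0.7, 0.9 were 1.53, 1.32, 1.16, 1.04 (k = 1, complete); 1.99, 1.73, 1.59, 1.64 (k = 0.8, complete); and 1.47, 1.34, 1.25, 1.46 (k = 1, 90% follow-up).

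For skewed outcomes with assumed distributions (6,000 trials, no effect), ratios at latent rho 0.3, 0.5, 0.7 were 1.71, 1.52, 1.38 for overdispersed counts and 1.67, 1.53, 1.40 for log-normal dollars. Type I error at 0.05 was 0.042 to 0.055 for the planned test and 0.033 to 0.044 for regression with HC3 standard errors.

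**The case against.** The planned test is valid and unbiased, puts all outcomes in one framework, and misses no stated precision target. Effect-size estimation is one of several pilot goals. The size of any gain rests on an unknown rho and unknown SDs. All of this is true, and it is why the point is a recommendation and not a correction.

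The more telling objection is that the figures in Step 5 are large-sample. Simulating the regression at 50 per arm with HC3 errors and a t reference gives power of about 41%, 52% and 74% at rho 0.3, 0.5, 0.7, against about 28%, 41% and 69% planned. That stands: the gain is smaller, though in the same direction. About half of the gap from the large-sample figures comes from using t instead of z.

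The gain can also vanish. At k = 1.25 and rho = 0.8 the formula gives (2.5625 − 2.0)/(1.5625 × 0.36) = 1.00. Simulation there gave a ratio of 0.992 and power of 68% for HC3 regression against 73% planned. At k = 1.25 and rho = 0.7 power was 48% against 52 to 53%, with the HC3 interval about 3% wider. At k = 1 and rho = 0.9 it was about 1% wider. So the claim that the planned contrast is never more precise holds for large-sample variance, not for every interval at N = 100.

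Finally, a GEE constrained to equal baseline means would be a smaller change. With a common scale its implied slope is 2·rho·k/(1 + k²) instead of rho·k. At k = 0.8 or 1.25 its variance exceeds the regression's by 0.5%, 1.6% and 4.6% at rho 0.3, 0.5, 0.7, and by about 20% at 0.9. It is a near equivalent at moderate rho, but not in general. It also needs a non-independence working correlation: under independence, dropping the arm main effect leaves only the month-3 comparison.

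**Conclusion.** The point holds. For four of the eight primary outcomes, and six if lapses and dollars are treated as continuous, the planned contrast has a large-sample variance at least as large as that of the baseline-adjusted regression. With equal SDs and complete data the excess is 54%, 33%, 18% and 5% at rho 0.3, 0.5, 0.7 and 0.9. It is larger if month-3 SDs are smaller than baseline SDs, and close to nil if they are about 1.25 times larger with rho near 0.7 to 0.8. The result relies on the planned 1:1 allocation, on linear models and, for the missing-data figures, on month-3 values missing completely at random. Validity of the planned test assumes cluster-robust standard errors, which the SAP implies but does not name. No result would be biased by leaving the plan as it is; the change is worth making because it is nearly free.

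**What to change.** - For the linear-model primary outcomes only, make the primary analysis a linear regression of the month-3 value on arm and the baseline value of the same outcome, with robust standard errors (HC3, for example). Report the arm coefficient.
- Keep the arm-by-time GEE as a sensitivity analysis and name its variance estimator.
- Leave food and utility security on the planned logistic models.
- State whether lapses and dollars are treated as continuous.
- The regression drops anyone without a month-3 value, so carry the missing-data methods over to it. The protocol says: "We will evaluate sensitivity to missing data by inverse probability of weighted GEE and multiple imputation". The SAP would consider weighting and "multiple imputation to handle missing data (e.g., due to loss to follow-up) if the amount is greater than 10" percent. Include arm and the baseline outcome in the weight and imputation models.

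The cost is a dated amendment to the SAP and protocol and re-specified weighting and imputation. No participants, visits or measurements are added. The amendment must precede any comparison of outcomes by arm. The SAP's Instructions show an X at the milestone for beginning analysis, so that point may have passed. If it has, report the regression as a labelled additional analysis.

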**End of File**
